1.2 Secondary Objectives

Phase Ib

1. To determine the composite CRc rate including CR + CRp + CRI within 3 months of treatment initiation in FLT3-ITD mutated patients with relapsed/refractory AML.
2. To determine the overall response rate (ORR) including CRc + partial remission (PR) within 3 months of treatment initiation in FLT3-ITD mutated patients with relapsed/ refractory AML.
3. To determine the duration of response (DOR), progression free survival, event-free survival (EFS), overall survival (OS), and number of patients bridged to hematopoietic stem cell transplant (HSCT) and median duration to HSCT from the initiation of the combination in FLT3-ITD mutated patients with relapsed/ refractory AML.
4. To characterize the pharmacokinetic (PK) profiles of combination therapy of venetoclax and quizartinib in FLT3-ITD mutated patients with relapsed/refractory AML..

Phase II

1. To determine the ORR within 3 months of treatment initiation in FLT3-ITD mutated patients with relapsed/ refractory AML.
2. To determine the DOR, PFS, EFS, OS, and number of patients bridged to HSCT and median duration to HSCT from the initiation of the combination in FLT3-ITD mutated patients with relapsed/ refractory AML.
3. To determine the safety and tolerability of the combination in FLT3-ITD mutated patients with relapsed/ refractory AML.

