5.1 Schedule

All patients will be registered through CORe.

The Phase Ib dose escalation stage of the study will evaluate the safety, tolerability, PD and PK of venetoclax in combination with quizartinib, with the objectives of identifying the MTD and RP2D for each combination.

Quizartinib will be administered orally daily continuously starting on cycle 1 day 1. Patients will self-administer quizartinib tablets orally QD. If a dose is missed or vomited, the next dose should not be increased to account for missing a dose. The subject should take the next regular dose at the regularly scheduled time. Patients will receive one cycle of therapy every 28 days (+/- 7 days). Cycle 1 Day 1 of each cycle will be counted from the start of the quizartinib dosing. Quizartinib dose escalation criteria will be maintained as suggested in quizartinib Investigational Brochure (IB) as follows:

1. If the target dose for the given patient in the phase IB or phase II portion is quizartinib 30mg the patient will start the dosing on C1D1 at quizartinib 30mg per day
2. If the target dose for the given patient in the phase IB or phase II portion is quizartinib 60mg the patient will start the dosing on C1D1 at quizartinib 30mg per day and can increase to quizartinib 60mg per day on C1D12 only if QTcF on triplicate ECG is <450 msec on the Day 12 post-dose EKG

The initiation of venetoclax will be deferred for 7 days in cycle 1 to allow clinical and correlative evaluation of quizartinib single agent activity, and to debulk tumor burden thereby reducing the risk of tumor lysis syndrome (TLS). The intent is to initiate venetoclax on cycle 1 day 8. Blood samples will be collected at pre-dose, 2 (+/- 30 minutes), 4 (+/- 30 minutes), 6(+/- 30 minutes), 8 (+/- 30 minutes) and 24 (+/- 30 minutes) hours post-dose on cycle 1 day 14 to measure venetoclax, quizartinib and AC886 concentrations in patients enrolled in the dose-escalation period (n=12). The WBC count must be <10K prior to the initiation of venetoclax dosing. Note: Hydroxyurea can be used if needed during these initial 7 days to control WBC count, if needed.

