5.5.7 DRUG DRUG INTERACTION ASSESSMENT

Both quizartinib and venetoclax are CYP3A and Pgp substrates. Both quizartinib and venetoclax are Pgp inhibitors, and the latter also inhibits BCRP. Therefore, the potential for a two way drug drug interaction will be assessed in a substudy of the first 12 subjects enrolled in the Phase 1b. Specifically this substudy will assess the effect of venetoclax on quizartinib PK (i.e. Cmax and AUC0-24h) and the effect of quizartinib on venetoclax PK (i.e. Cmax and AUC0-24h) as summarized in section 5.1.

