Bone marrow samples:

- At screening (within 14 days preceding study initiation) as per section 7.1.8 – This BM will be done after the patient is consented to the study
- Cycle 1 day 8 (prior to the first dose of venetoclax)
- At the time of disease assessment on day 28 (+/- 4 days)
- At response assessment pre-cycle 4 (EOC 3)
- At progression/relapse (if sample available)
- Missed samples or cycles outside the provided time windows for correlative studies and/or for PK analysis will not constitute

protocol deviations. These studies are optional on this protocol.

7.2.10 All treatment prescriptions for quizartinib and venetoclax must be written by the patient's attending physician at MDACC or the PI of the study. We do not intend for the subjects to receive prescriptions for quizartinib or venetoclax at an outside physician's office. During the first cycle all the protocol required laboratory evaluations will be done at MDACC. Subsequently, the patient may have the laboratory work done at a local clinic and the results reported to the research nurse for the study. The laboratory work done at the local clinic will be forwarded to the patient's attending physician at MDACC or PI of the study, who will sign off on the labs to verify that the results have been reviewed.

Outside Physician Participation During Treatment

1. MDACC Physician communications with the outside physician is required prior to the patient returning to the local physician. This will be documented in the patient record.
2. A letter to the local physician outlining the patient's participation in a clinical trial will request local physician agreement to supervise the patient's care.
3. Protocol required evaluations outside MDACC will be documented by telephone, fax or e-mail. The PI/treating physician must review the labs, determine clinical significance and sign and date the report.
4. A copy of the informed consent, protocol abstract, treatment schema and evaluation during treatment will be provided to the local physician.
5. Documentation to be provided by the local physician will include progress notes, reports of protocol required laboratory and diagnostic studies and documentation of any hospitalizations.
6. The home physician will be requested to report to the MDACC physician investigator all life threatening events within 24 hours of documented occurrence.
7. All follow-up visits that correspond with drug dispensation will be performed at MDACC.

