11.1 Phase Ib (Lead-in Phase)

The phase Ib portion is aimed at finding the MTD and RP2D of the two drugs in this combination. We plan to select a RP2D based on efficacy, toxicity, and PD data from the phase 1b dose-escalation. 3 patients at each dose level may not be sufficient to get a good estimate of efficacy and PD changes, and thus 6 patient dose escalation schema is proposed.

Patients will be enrolled in cohorts of 6 patients in the phase Ib portion of the study. The target dose is dose level +1, and the starting dose will be dose level 0. The first 6 patients on study will receive dose level 0.

The MTD is defined as the highest dose level with ≤ 1 out of 6 patients experience a DLT during the first 28 days of treatment. DLT is defined in section 3.4. The planned dosing algorithm is presented in section 3.3 and the dosing schema for the combination treatment is shown in Table 1. The RP2D will be selected at the end of the phase I portion based on reviewing the safety, efficacy, and PD data of quizartinib and venetoclax after discussion between the PI/Co-PI, the sponsor (MDACC IND office), and the supporting companies (Daiichi-Sankyo and Abbvie Inc). The Investigator is responsible for completing the cohort summary template prior to advancing subjects to the phase II part. Once RP2D has been established, any patients still on study at a dose lower than RP2D can be dose escalated up to RP2D in accordance with the dose-escalation guidelines in section 5.2.3.

The PK of quizartinib will be summarized statistically as n, geometric mean, %CV, median, minimum and maximum as Cmax and AUC0-24h of quizartinib and AC886 collected on Cycle 1 Day 7 (quizartinib alone) and Cycle 1 Day 8 (quizartinib + venetoclax) for the first 12 subjects. PK parameters will be dose normalized.

The PK of venetoclax will be summarized statistically as n, geometric mean, %CV, median, minimum and maximum for Cmax and AUC0-24h of venetoclax and M27 collected on Cycle 1 Day 8 (venetoclax + quizartinib) for the first 12 subjects. PK parameters will be dose normalized.

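### PK is a phase Ib secondary objective planned in the first 12 subjects, but section 7.2.9 excuses missed PK samples and, read plainly, makes PK optional

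*Combined protocol and SAP*

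**What the plan says.** - **Section 1.2** lists as phase Ib secondary objective 4: "To characterize the pharmacokinetic (PK) profiles of combination therapy of venetoclax and quizartinib".
- **Section 5.1** schedules six samples on cycle 1 day 14, from pre-dose to 24 hours, to measure both drugs and AC886 "concentrations in patients enrolled in the dose-escalation period (n=12"). It mentions no option to decline.
- **Section 5.5.7** notes that both drugs are CYP3A and P-gp substrates and P-gp inhibitors, so "the potential for a two way drug drug interaction will be assessed in a substudy of the first 12 subjects enrolled in the Phase 1b".
- **Section 11.1** summarises quizartinib and AC886 Cmax and AUC0-24h from cycle 1 day 7 ("quizartinib alone) and Cycle 1 Day 8 (quizartinib + venetoclax) for the first 12 subjects"), and venetoclax from day 8. The summary is descriptive: n, geometric mean, %CV, median and range, dose-normalised.
- **Section 7.2.9**, in its last bullet, says that missed or out-of-window samples "for correlative studies and/or for PK analysis will not constitute" "protocol deviations. These studies are optional on this protocol".
- **Sections 3.3 and 3.4** replace patients who leave before day 28 without a DLT for reasons other than toxicity, and patients who received less than 75% of either drug without a DLT. Neither section mentions missing PK.

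**The concern.** Four sections treat PK as part of the plan for a fixed set of 12 subjects. The only sentence in section 7 that mentions PK excuses its absence, and the next sentence calls these studies optional. Staff who work from the section 7 evaluation schedule find no PK draws listed and have no reason to treat them as required.

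At stake is a secondary objective and the only planned PK sampling of the combination. The plan sets no minimum number of PK-evaluable subjects and no rule for missing profiles. The number of profiles behind the interaction assessment is therefore left to chance.

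**Working it through.** **1. The planned number.** Section 3.3 allows two cohorts of six: 2 × 6 = 12. This reproduces the 12 in sections 5.1, 5.5.7 and 11.1. The documents give no power or precision calculation for PK, so there is none to reproduce.

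**2. Does optional cover PK?** The opening of 7.2.9 attaches the word to pharmacodynamic studies as defined in section 6.0, and section 6.0 contains no PK. But the sentence immediately before the optional statement names correlative studies and PK analysis together. The plain referent includes PK. On the milder reading PK is not optional, but the deviation waiver still covers it.

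**3. How many profiles might there be?** The documents give no participation rate. With assumed rates p, independent across 12 subjects:

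| p (assumed) | Expected profiles, 12p | P(all 12) = p^12 |
|---|---|---|
| 0.90 | 10.8 | 28% |
| 0.75 | 9 | 3.2% |
| 0.50 | 6 | 0.02% |

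**4. Illustrative precision of a geometric mean.** Input: the %CV of steady-state quizartinib AUC0-24h at 30 mg is 72.5% (section 2.2). On the log scale, SD = sqrt(ln(1 + 0.725²)) = 0.650. The 95% confidence factor is exp(t(0.975, n−1) × 0.650 / sqrt(n)).

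- n = 12: exp(2.201 × 0.650 / 3.464) = 1.51
- n = 9: exp(2.306 × 0.650 / 3) = 1.65
- n = 6: exp(2.571 × 0.650 / 2.449) = 1.98

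This CV is borrowed. With a half-life near 100 hours, day 7 is not steady state: its 24-hour sample falls 168 hours after the first dose, about 1.7 half-lives.

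**5. The within-patient contrast.** The effect of venetoclax on quizartinib is a within-patient ratio, which step 4 does not describe. The documents give no within-patient CV. At an assumed 30%, log SD = sqrt(ln 1.09) = 0.294, and the 90% confidence factor exp(t(0.95, n−1) × 0.294 × sqrt(2/n)) is 1.24, 1.29 and 1.41 for n = 12, 9 and 6. With all 12 profiles, assumed CVs of 20% to 50% give 1.16 to 1.41.

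**6. Sampling days.** Section 5.1 samples on day 14 only, after venetoclax has started on day 8. Section 11.1 analyses days 7 and 8. Sampling under 5.1 alone yields no quizartinib-alone profile, so the contrast in step 5 could not be formed even with 12 complete profiles.

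**The case against.** The strongest reply is that the sections can be read together. The opening of section 7.0 says that occasional missed required research samples are not deviations, so a waiver does not by itself make a sample optional. The opening of 7.2.9 limits optional to pharmacodynamic work, and the consent pages are not available to show whether patients may decline PK. This stands as far as it goes: a reader might infer that the sections flatly cannot both hold, and the documents do not force that. They do leave the status of PK unclear where staff would look for it.

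Other stronger readings also go beyond the documents:

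- **Nothing replaces a lost profile.** Patients replaced under 3.3 or 3.4 may contribute PK. What is true is that missing PK alone triggers no replacement.
- **Those who tolerated treatment would be over-represented.** This is plausible for day 14, which falls after the projected inpatient stay of days 7 to 12 (section 5.5.4). It is less so for days 7 and 8, which fall within that stay. No passage links missed draws to tolerability.
- **The phase II dose rests on PK.** Sections 3.3, 3.5 and 11.1 name efficacy, safety and pharmacodynamics. PK has no hypothesis, margin or decision rule, and QTc is monitored separately by scheduled ECGs.
- **The 60 mg CV (95.7%) shows a larger loss.** Under 5.1, patients with a 60 mg target start at 30 mg and can increase only on day 12. None of days 7, 8 and 14 is 60 mg steady state. The first six patients are at level 0, so 12 such profiles cannot arise.

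**Conclusion.** The point holds as an inconsistency that can reduce the PK data. It is not a demonstrated bias or a threat to dose selection. PK is planned in 12 subjects for a secondary objective and the interaction assessment, while 7.2.9 waives missed samples and, read plainly, makes them optional. The result could rest on fewer than 12 profiles.

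If half were missing, the confidence factor for a between-patient geometric mean would go from 1.51 to 1.98 at the 30 mg CV. That figure is illustrative: it assumes log-normal exposure and the borrowed steady-state CV, and six profiles is an assumed outcome. The within-patient figures rest on an assumed CV. The mismatch between day 14 and days 7 and 8 must be settled at the same time, since complete sampling on day 14 alone would not supply the comparison that section 11.1 describes.

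**What to change.** 1. In 7.2.9, confine both the optional statement and the deviation waiver to the section 6.0 correlatives.
2. State there that PK sampling is required for the first 12 phase Ib subjects, and list the draws in the section 7 schedule.
3. Reconcile the PK days in 5.1 and 11.1 so that the required profiles include the quizartinib-alone sample that 11.1 analyses.
4. In 11.1, report the number of missing profiles and the reasons by dose level. The planned n gives the count analysed but not who is missing or why.

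If the sponsor does intend PK to be optional, sections 5.1, 5.5.7 and 11.1 should say so and set a minimum number of PK-evaluable subjects.

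The cost is a few sentences. PK draws are already planned for these 12 patients, though step 3 may change or add sampling days. The real downside is that phase Ib patients could no longer decline serial PK draws.

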8.0 CRITERIA FOR RESPONSE

Response criteria will be modified from the International Working Group for AML(52). Responders are patients who obtain a Composite Complete Remission Rate (CRc) with or without cytogenetic response, hematologic improvements, and morphologic leukemia-free state. CRc rate is defined as the confirmed remission rate of all complete and incomplete CRs (i.e., CR+ CRp + CRi).

8.1 Complete Remission (CR)

For patients to be classified as being in CR, they must have bone marrow regenerating normal hematopoietic cells and achieve a morphologic leukemia-free state and must have an ANC $> 1 \times 10^9/L$ and platelet count $\geq 100 \times 10^9/L$, and normal marrow differential with $< 5\%$ blasts, and patients will be red blood cell (RBC) and platelet transfusion independent (defined as 4 weeks without RBC transfusion and 1 week without platelet transfusion). There should be no evidence of extramedullary leukemia.

8.2 Complete Remission with Incomplete Platelet Recovery (CRp)

For patients to be classified as being in CRp, they must achieve CR except for incomplete platelet recovery ($< 100 \times 10^9/L$).

8.3 Complete Remission with Incomplete Hematological Recovery (CRi)

For patients to be classified as being in CRi, they must fulfill the criteria for CR except for incomplete hematological recovery with residual neutropenia (ANC $\leq 1 \times 10^9/L$) with or without thrombocytopenia (platelet count $< 100 \times 10^9/L$). In addition, patients do not need to be RBC or platelet transfusion independent (modification to Cheson criteria).

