5.3 Duration of Therapy

In the absence of treatment delays due to adverse events, treatment may continue until one of the following criteria applies:

1. Clinically significant progressive disease, or
2. Grade 4 QTc prolongation (based on average of triplicate).
3. Intercurrent illness that prevents further administration of treatment, or
4. Patient request, or
5. General or specific changes in the patient's condition render the patient unacceptable for further treatment in the judgment of the investigator, or
6. Unacceptable toxicity that in the opinion of the investigator makes it unsafe to continue therapy. This includes patients with grade 4 non-hematological toxicity unless it reverses to grade ≤ 1 on or before 8 weeks of interrupting quizartinib and/or venetoclax.

5.3.1 It is planned that up to a total of 24 cycles of therapy will be administered for patients deriving benefit from this regimen. Continuation of therapy for patients completing 24 cycles of therapy may be considered on a case-by-case basis after discussion with the principal investigator.

5.3.2. All patients receiving at least one dose of either of the two drugs will be considered evaluable for toxicity.

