8.8 Best Response measurement

Response will be measured and defined for primary endpoints as the best response achieved during the first 3 cycles of therapy, or at time off study, for those patients discontinuing treatment before the completion of 3 cycles of therapy. Best response is defined to be the best-measured response (CRc=CR+CRp+CRi, PR, or marrow clearance) post-treatment up to that time. Best response will also be evaluated for the full treatment period using all assessments up to and including treatment discontinuation.

9.0 DISCONTINUATION OF TREATMENT:

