11.3 Statistical Analysis Plan

All patients who receive any dose of the study agent will be included in the analysis for efficacy and safety. We will follow standard reporting guidelines for adverse events, and summarize safety data by category, severity and frequency. For the primary efficacy analysis, we will estimate the CRc rate for the combination treatment, along with the 95% credible interval. Patients who drop out of the study before completing all the cycles will be treated as “failures” for the primary analysis.

Patients’ demographic and clinical characteristics will be summarized using descriptive statistics. Specifically, categorical covariates will be summarized by frequencies and percentages and their associations with responses will be assessed using Fisher’s exact test or its generalization. Continuous covariates will be summarized by means, standard deviations, medians and ranges, and the difference between responses groups will be assessed using the Wilcoxon rank sum test. Paired t-tests or Wilcoxon signed-rank tests will be used to determine the immunological and molecular changes in the peripheral blood and bone marrow from baseline to the time of response, and to the time of disease progression.

We will estimate the rates of partial response and bone marrow blast reduction $\geq 50\%$ within 3 months, along with 95% confidence intervals. For each subject, duration of response (DOR), event-free survival time and overall survival time will be calculated. DOR is defined as the time period from the first documentation of CRc to disease

recurrence, disease progression, or death whichever occurs first. Event-free survival time is defined as the time period from the date of treatment initiation to the date of documented treatment failure, relapses from CRc, or death from any cause, whichever occurs first. The observed DOR/EFS will be censored at the last follow-up if the patient is alive and no events observed. The overall survival time is defined as the time duration from treatment start till death or last follow-up if the patient is alive. The distributions of time-to-event endpoints including OS and DOR will be estimated using the Kaplan-Meier method. Comparisons of time-to-event endpoints by important covariate subgroups will be made using the log-rank tests. Progressive disease will be determined using ELN (2017) recommendations and is defined as any one or more of the following:

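### As defined, CRc is not monotone in count recovery: after a recent RBC transfusion, a marrow remission with ANC ≤1 counts as CRi but one with ANC >1 falls outside CRc; separately, the PR definition contradicts itself

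*Combined protocol and SAP*

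**What the plan says.** CRc is CR + CRp + CRi: "CRc rate is defined as the confirmed remission rate of all complete and incomplete CRs" (8.0). It is the Phase II primary endpoint, at any time in the first three cycles, and drives the Table 4 futility rule (11.2).

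- **CR (8.1):** ANC >1 × 10⁹/L, platelets ≥100 × 10⁹/L, marrow blasts <5%, and "patients will be red blood cell (RBC) and platelet transfusion independent (defined as 4 weeks without RBC transfusion and 1 week without platelet transfusion".
- **CRp (8.2):** "they must achieve CR except for incomplete platelet recovery", meaning platelets <100.
- **CRi (8.3):** "they must fulfill the criteria for CR except for incomplete hematological recovery with residual neutropenia" (ANC ≤1), with or without platelets <100. It then adds: "In addition, patients do not need to be RBC or platelet transfusion independent (modification to Cheson criteria".
- **PR (8.4):** at least a 50% fall in marrow blasts, to between 5% and 25%, and the criteria for CR met as well.

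On timing and early leavers, 8.8 takes "the best response achieved during the first 3 cycles of therapy, or at time off study". Section 11.3 says "Patients who drop out of the study before completing all the cycles will be treated as" failures, without saying how many cycles that means. Section 5.3.1 reads: "It is planned that up to a total of 24 cycles of therapy will be administered".

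**The concern.** A composite remission endpoint should not lose a success because a blood count improved. Here the transfusion waiver is available only to neutropenic patients. At a given assessment, neutrophil recovery can therefore move a transfused patient from counted to not counted, in both the primary endpoint and the futility count. The waiver is marked as a deliberate modification; the problem is that it depends on ANC.

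Two drafting conflicts sit beside it. The PR definition cannot be met as written, and PR enters the secondary ORR endpoint (1.2). Sections 8.8 and 11.3 also give different rules for patients who leave early, so the same patient could be a success under one and a failure under the other.

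**Working it through.** **1. Classification.** Take a marrow with <5% blasts and all other CR marrow and extramedullary criteria met. Cross ANC (>1, ≤1), platelets (≥100, <100), RBC transfusion in 4 weeks (no, yes) and platelet transfusion in 1 week (no, yes). This gives 16 cells.

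| | ANC ≤1 | ANC >1 |
|---|---|---|
| No recent transfusion, platelets ≥100 | CRi | CR |
| No recent transfusion, platelets <100 | CRi | CRp |
| Platelet transfusion only, platelets ≥100 | CRi | none |
| Platelet transfusion only, platelets <100 | CRi | ambiguous |
| RBC transfusion (4 cells: either platelet count, with or without platelet transfusion) | CRi | none |

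All 8 cells with ANC ≤1 are CRi. With ANC >1 there are 1 CR, 1 CRp, 5 outside CRc and 1 ambiguous. In the ambiguous cell, incomplete platelet recovery in 8.2 could be read to cover a recent platelet transfusion. The RBC cells are not ambiguous. Morphologic leukemia-free state and hematologic improvement are named among responses in 8.0, and marrow clearance in 8.8, but none is part of CRc.

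**2. Who is lost.** Only a patient with no qualifying assessment in the first three cycles (8.8, 11.2). The first scheduled marrow is day 28 ± 7 (7.2.6). At a marrow on or before day 28 the 28-day look-back reaches day 28 − 28 = 0 or earlier, so any RBC transfusion since treatment start puts a patient with ANC >1 in the gap at that point. Three 28-day cycles last 84 days, which leaves 84 − 28 = 56 days in which to complete 28 RBC-free days. Another marrow is due at the end of cycle 3, and extra marrows are allowed. The documents give no share of patients who stay in the gap throughout.

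**3. The plan's own figures.** Under 11.2 the prior is Beta(0.5, 1.5), so after x responses in n the posterior is Beta(0.5 + x, 1.5 + n − x). Accrual stops if Pr(CRc > 0.25 + 0.25 | data) < 0.025.

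| Count | Pr(CRc > 0.50) | Decision |
|---|---|---|
| 2/10 | 0.0149 | stop |
| 3/10 | 0.0640 | continue |
| 4/15 | 0.0210 | stop |
| 5/15 | 0.0656 | continue |

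This agrees with Table 4. With response and toxicity independent, exact calculation gives 0.1605 early stopping at CRc 50% and toxicity 30%, and all 25 cells of Table 6 reproduce to within 0.0001.

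**4. Effect of one patient.** Posterior mean = (0.5 + x)/22 at n = 20.
- 10/20: 10.5/22 = 47.7%
- 9/20: 9.5/22 = 43.2%
- difference: 1/22 = 4.5 points

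At a look, counting a gap patient who is literally excluded turns 2/10 into 3/10 or 4/15 into 5/15 (stop becomes continue). Removing one who was counted on a broad reading does the reverse.

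The chance that the trial reaches such a count is a property of the design:
- **At the boundary, true CRc 50%:** P(2/10) = 0.0439. P(continue at 10, then 4/15) = 0.1172 × 0.1563 + 0.2051 × 0.0313 = 0.0247. Total 6.9%; the same sum at 25% gives 41.5%.
- **One above it, at either look:** 15.7% at 50% and 32.2% at 25%.

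These apply to any one-patient scoring dispute. None is the probability that this defect changes a decision, which also needs the unknown chance of a gap patient.

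**5. PR.** Section 8.4 needs blasts of 5–25% and the CR criteria; 8.1 needs <5%. No value satisfies both. Read literally PR is empty and ORR (CRc + PR) equals CRc. Yet 8.7 defines relapse after PR, 8.8 lists PR as a best response and 11.3 estimates its rate.

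**6. Early leavers.** A patient with CRi in cycle 1 who leaves in cycle 2 is a success under 8.8 and a failure under 11.3. If all the cycles means 24, a responder who leaves after cycle 3 is also a failure under 11.3. Where 11.3 governs, the gap costs an early leaver nothing further.

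**The case against.** The strongest reply is that best response over three cycles rescues many patients. Counts are taken at least twice weekly (7.2.3), and no passage ties transfusion status to marrow dates only. That stands: it limits the number affected, though it does not make the definition coherent. It can also be said that for the RBC case the letter is clear, so two adjudicators following the text would agree. That stands too; only the platelet-transfusion-only cell is open. The PR wording is probably a slip for the CR blood-count criteria, and it touches secondary endpoints only. That is plausible, but the text does not say so.

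Three stronger readings are tempting and not supported:
- **That the gap raises early stopping above 16.1%.** This would require the 50% target to mean marrow remission regardless of transfusion, and a share of patients in the gap. Section 11.2 states the target as CRc, and the documents give no share. With CRc as literally defined, Table 6 is unchanged.
- **That CRc is biased downward against 25%.** The transfusion rule behind the historical rate is not given, so neither direction can be claimed.
- **That the case report form lacks transfusion data.** Table 3 lists transfusions with concomitant medications and therapies, and 7.2.7 keeps concomitant medication data off the form apart from first-cycle hydroxyurea. But Table 3 gives instructions for use, and no passage places transfusions under that exclusion. Section 5.5.1 also has cytarabine recorded, so 7.2.7 is not a full account of the form.

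**Conclusion.** The point holds as a defect of definition. Following 8.1–8.3 exactly, better neutrophil recovery can remove a transfused patient from the primary endpoint, and nothing elsewhere closes the gap. Its size can be stated only per patient: 4.5 points on the posterior mean at n = 20, and a possible change of futility decision at the boundary or one above it. The number of patients affected is unknown, and Tables 4–6 are correct for the rules they state. The PR contradiction is certain on the text and affects secondary analyses. The conflict between 8.8 and 11.3 over early leavers reaches the primary endpoint directly. It should be fixed, at modest cost. The conclusion rests on the literal wording of section 8 and assumes no frequency of transfusion.

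**What to change.** 1. Reconcile 8.1–8.3 so that one transfusion rule applies whatever the ANC, and a patient counted at worse counts is also counted at better ones. One form: CRi is CR except for residual neutropenia, thrombocytopenia or transfusion independence, singly or together, and not meeting CRp. State whether a platelet transfusion in the past week with platelets <100 is compatible with CRp.
2. Make the reworded CRc primary only if the sponsor confirms that the 25% reference used a comparable transfusion rule. Otherwise keep the literal definition for the primary endpoint and Table 4, settle the platelet-only case in writing, and report the broadened CRc as a sensitivity analysis.
3. Reword 8.4 so that PR does not require the CR marrow-blast and leukemia-free-state criteria, and state which CR blood-count criteria apply.
4. Reconcile 8.8 with 11.3 for patients who leave before completing three cycles, and define all the cycles.
5. Confirm that adjudicators have the transfusion dates needed to apply 8.1–8.3.

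Cost: wording in 8.1–8.4, 8.8 and 11.3, and one sensitivity analysis. Sample size and Tables 4–6 do not change if the literal definition stays primary. The downside of a broader primary CRc is that it could favor success if the 25% reference used a stricter rule, which is why it depends on the sponsor's confirmation.
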